4.6 Analyses of biochemical efficacy

Biochemical efficacy of anacetrapib 100 mg daily will be assessed in non-fasting specimens taken from all participants at the randomization visit, at the 2 month follow-up visit, at a follow-up visit when median follow-up is about 2 years and at the final study visit. In addition, samples will be taken annually in 5% of participants. The following biochemical efficacy outcomes will be measured using standard automated assays on all samples:

- total cholesterol
- HDL cholesterol
- LDL cholesterol
- non-HDL cholesterol
- triglycerides
- apolipoprotein A1
- apolipoprotein B

In addition, lipoprotein (a) is to be measured in all participants at randomization and at about 2 years after the median participant is randomized, and in at least 5% of participants annually.

[°] For the purposes of these analyses, rhabdomyolysis is defined as CK>40x ULN with muscle symptoms or CK>10x ULN with evidence of end-organ damage such as doubling of serum creatinine

Samples of genetic material, plasma, serum, and urine have been biobanked for possible future analyses.

The effect of anacetrapib on other aspects of lipid and lipoprotein profile (such as lipoprotein particle size) may also be examined. In particular, a sub-study is comparing the assessment of LDL cholesterol using a direct method (which is used routinely for REVEAL samples) with a beta quantification method among around 2000 samples taken at 2 years of follow-up. The results of this sub-study may inform the interpretation of the main analyses of the effect of anacetrapib on LDL cholesterol concentration.

4.7 Exploratory assessments

Exploratory assessments will be made of other possible beneficial or adverse effects of anacetrapib during the scheduled treatment period. Examples include all serious adverse events and all non-serious adverse reactions, both overall and categorised by assigned System Organ Class (see section 5.6). Other analyses will include disturbances of cardiac rhythm (atrial fibrillation/flutter; ventricular tachycardia/fibrillation), mood (assessed using the Mental Health Inventory [MHI]-5 questionnaire), and cognitive function (assessed using the Modified Telephone Interview for Cognitive Status [TICS-M] questionnaire). Additional exploratory analyses may be undertaken, as considered appropriate, and cautiously interpreted (see section 5.2 for approaches to handling multiple hypothesis testing). These may include exploration of the effects of anacetrapib on additional clinical outcomes over time (e.g. ≤ 1 year vs > 1 year post-randomization) or in particular sub-groups of participant (e.g. high HDL-cholesterol or low LDL-cholesterol at randomization). The results of the REVEAL trial will also be considered in the context of information from randomized clinical trials of the effects of other lipid-modifying drugs (e.g. statins, ezetimibe) on cardiovascular events. In addition, a sub-study is assessing the concentration of anacetrapib in serial measures of blood and adipose tissue in around 500 individuals. The results of this sub-study may inform the interpretation of the analyses of possible beneficial or adverse effects of anacetrapib on clinical outcomes.

4.8 Health economic assessments

Appropriate health economic assessments regarding the use of anacetrapib among patients at risk of vascular events will be conducted. Analyses of EQ5D questionnaires recorded at randomization and final follow-up visits will be used to determine the effects of clinical outcomes on quality of life. The detailed analysis plan for health economic assessments is outside the remit of this document.

5 Details of analyses

5.1 Methods of analysis

All participants randomized to anacetrapib will be compared with all participants randomized to placebo, regardless of whether a participant received all, some or none of their allocated treatment (i.e. intention-to-treat [ITT] analyses).^{2,3} A participant may contribute to more than one assessment if they have events of more than one type (e.g. non-fatal ischaemic stroke followed by coronary death). For the time-to-event analyses, survival analytic methods will be used to evaluate the time to the first event during the entire study period. For each outcome, log-rank method will be used to estimate the average event rate ratio comparing all those allocated active anacetrapib with all those allocated placebo.³ Estimates of the event rate ratio will be shown with 95% confidence intervals. Kaplan-Meier estimates for the time to each of the primary and secondary outcomes will also be plotted (with their associated log-rank p-values). Cox regression may be used where rate ratios are extreme (e.g. > 2 or < 0.5). In all analyses, two-sided p-values (2P) < 0.05 will be considered statistically significant (after any allowance for multiplicity as outlined in section 5.2).

Recurrent events will be analysed using the negative binomial and sensitivity analyses will be performed using alternative methods such as the Andersen-Gill approach.

At the time of finalizing the Data Analysis Plan in May 2016, around 99% of the 28,613 surviving randomized participants had attended their most recent scheduled visit. Since loss-to-follow-up at study end is anticipated to be minimal (<1%), no exploratory analyses investigating the impact of missing data not at random/informative missingness are planned.

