4.1 Primary assessment

The primary assessment will involve an intention-to-treat comparison among all randomized participants of the effects of allocation to anacetrapib versus placebo on the incidence of major coronary events (defined as the occurrence of coronary death, myocardial infarction or coronary revascularization procedure) during the scheduled treatment period.

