4.2 Secondary assessments

Secondary assessments will involve intention-to-treat comparisons among all randomized participants of the effects of allocation to anacetrapib versus placebo during the scheduled treatment period on:

- (i) Major atherosclerotic events (defined as coronary death, myocardial infarction or presumed ischaemic stroke; the key secondary outcome);
- (ii) Presumed ischaemic stroke (i.e. not known to be haemorrhagic); and

^a Following investigation of a serious breach of good clinical practice at one centre (centre id 3314), the Steering Committee determined (blind to knowledge of any unblinded results) at its meeting in February 2014 that all data from this centre should be excluded from all analyses.

^b A single censoring date is to be used in the REVEAL analyses for both fatal and non-fatal events. The censoring date is to be determined according to the flow-chart in Appendix A. Censoring rule.

- (iii) Major vascular events (defined as coronary death, myocardial infarction, coronary revascularization or presumed ischaemic stroke).

In addition, each of the individual components of the primary outcome (i.e. coronary death; myocardial infarction; and coronary revascularization) will be tested separately.

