5.3 Tests for heterogeneity of effects

Tests for heterogeneity of the proportional effect observed in subgroups will be used (whilst controlling the false discovery rate to allow for multiple comparisons) to determine whether the proportional effects in specific subcategories are clearly different from the overall effect.^{2,3} If, however, patient categories can be arranged in some meaningful order (e.g. age at randomization: <65; ≥65<70; ≥70) then assessment of any trend will be made. Unless otherwise stated, those with missing values of baseline values will be included in the subgroup that includes the median (for continuous variables) or the largest group (for categorical variables), and the number of missing values will be clearly indicated.

When a number of different subgroups are considered, chance alone may lead to there being no apparent effect in several subgroups in which the effect of treatment really is about the same as is observed overall. In such circumstances, “lack of direct evidence of benefit” is not good “evidence of lack of benefit”, and clearly significant overall results would provide strong indirect evidence of benefit in some small subgroups where the results, considered in isolation, are not conventionally significant (or, even, perhaps, slightly adverse).^{2,3,5} Hence, unless the proportional effect in some specific subcategory is clearly different from that observed overall, the effect in that subcategory is likely to be best estimated indirectly by applying the proportional effect observed among all patients in the trial to the absolute risk of the event observed among control patients in that category.⁵

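### The Kaplan-Meier curves planned in SAP 5.1 censor deaths outside the outcome and so slightly overstate the proportion affected; cumulative incidence curves would correct the display

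*SAP*

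**What the plan says.** Section 5.1 rests inference on the log-rank analysis: the "log-rank method will be used to estimate the average event rate ratio", with 95% confidence intervals, and "two-sided p-values (2P) < 0.05 will be considered statistically significant" after any allowance for multiplicity. For display it adds that "Kaplan-Meier estimates for the time to each of the primary and secondary outcomes will also be plotted", each with its log-rank p-value. The SAP mentions neither cumulative incidence nor competing events.

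The outcomes to be plotted differ in the deaths they count:

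- The primary outcome (4.1) is "defined as the occurrence of coronary death, myocardial infarction or coronary revascularization procedure".
- The key secondary outcome (4.2) is "Major atherosclerotic events (defined as coronary death, myocardial infarction or presumed ischaemic stroke; the key secondary outcome". Major vascular events add coronary revascularization to that list.
- A further secondary outcome is "Presumed ischaemic stroke (i.e. not known to be haemorrhagic". It is not restricted to non-fatal strokes.
- Section 4.2 also has the components of the primary outcome tested one by one.

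Footnote b to 4.2 says that "A single censoring date is to be used in the REVEAL analyses for both fatal and non-fatal events"; the flow-chart that sets the date is not shown in the text at hand. Section 4.4(ii) analyses all-cause and cause-specific mortality separately. Section 5.3 recommends estimating the effect in a subgroup by applying the overall proportional effect to "the absolute risk of the event observed among control patients in that category".

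**The concern.** A participant who dies of a cause outside the outcome can no longer have the event. Kaplan-Meier knows only events and censoring. It therefore removes that participant as if the event could still have happened later, and describes a population in which nobody dies of anything else. One minus Kaplan-Meier is then at or above the proportion actually affected.

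These plots are the only time-based display of absolute risk that the SAP specifies, and readers tend to take absolute risks and differences from such plots. The error has one direction, and the data needed to remove it are already being collected, because deaths are classified by cause for section 4.4(ii).

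**Working it through.** The SAP states no absolute risk or competing-death figure, so there is no figure of its own to reproduce. The check sizes the effect under stated assumptions.

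**Direction.** Cumulative incidence adds up, over time, the event hazard times the probability of being both event-free and alive. One minus Kaplan-Meier uses the probability of being event-free with other deaths ignored, which is never smaller. The direction therefore needs no assumption. A rule that fixes the censoring date does not alter this.

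**Inputs from the SAP.** Over 30,000 randomized (2.1); 28,613 surviving at May 2016 (5.1); about 3 years' median follow-up in November 2015 and about 4 years scheduled (2.1).

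**Assumptions.** N is 30,000 to 31,000. Median follow-up at the survivor count, t, is 3.0 to 3.5 years. Hazards are constant. The share of deaths outside the outcome is 0.5-0.7 for the composites and up to 1.0 for stroke alone. Four-year event risk is 10-15% for the composites and 2-5% for stroke.

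**Step 1, deaths.** 30,000 - 28,613 = 1,387 (4.6%); 31,000 - 28,613 = 2,387 (7.7%).

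**Step 2, hazards.** Death hazard = -ln(1 - deaths/N)/t.
- Low case (N = 30,000, t = 3.5): 0.01352 per year. With share 0.5 the competing hazard hc is 0.00676.
- High case (N = 31,000, t = 3.0): 0.02671 per year. With share 0.7, hc is 0.01870.

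**Step 3, four-year risk.** With event hazard he = -ln(1 - plotted risk)/4, cumulative incidence = he/(he + hc) × (1 - exp(-4(he + hc))).

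Example, low case, 10% plotted: he = 0.02634, he + hc = 0.03310, and 0.02634/0.03310 × (1 - exp(-0.1324)) = 9.87%.

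| Outcome | Case | Plotted 1-KM | Cumulative incidence | Excess, points | Relative |
|---|---|---|---|---|---|
| Composite | low, share 0.5 | 10% | 9.87% | 0.13 | 1.3% |
| Composite | low, share 0.5 | 15% | 14.80% | 0.20 | 1.3% |
| Composite | high, share 0.7 | 10% | 9.64% | 0.36 | 3.7% |
| Composite | high, share 0.7 | 15% | 14.47% | 0.53 | 3.7% |
| Stroke alone | low, share 1.0 | 2% | 1.95% | 0.05 | 2.7% |
| Stroke alone | high, share 1.0 | 5% | 4.74% | 0.26 | 5.4% |

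The stroke rows are an upper bound on the competing share, because a fatal presumed ischaemic stroke is an event and not a competing death.

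**Step 4, difference between arms.** Assume a rate ratio of 0.90, a 10% control risk and equal competing hazards in both arms. By Kaplan-Meier the treated risk is 1 - 0.90^0.9 = 9.05%, a difference of 0.95 points. By cumulative incidence the difference is 0.94 points (low composite case) to 0.92 points (high composite case). The number needed to treat moves from about 105 to about 106-109. The ratio of risks changes by less than 0.0002.

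**The case against.** The strongest defence is that the plan is coherent as written. Kaplan-Meier, the log-rank test and the log-rank rate ratio all treat other deaths as censoring and all address the cause-specific hazard. A cumulative incidence curve also depends on any treatment effect on other deaths, and the log-rank p-value is not its test, so a straight swap would introduce a mismatch that the present text does not have. The effect is hardly visible on a plot, and 4.4(ii) already reports the competing deaths by allocation. All of this stands. It argues for adding a caption and for keeping the log-rank analysis. It does not make one minus Kaplan-Meier an estimate of the proportion affected.

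A reader might also infer more than the SAP supports:

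- *That the curves leave out most deaths.* The SAP gives no split by cause, and all the composites count coronary death.
- *That every death competes with stroke.* The definition covers fatal presumed ischaemic stroke.
- *That the control risks in 5.3 are inflated, most of all in high-risk subgroups.* Section 5.3 speaks of observed risk and does not say that it comes from Kaplan-Meier; a crude proportion would not carry this overstatement. Section 5.1 plans curves for the primary and secondary outcomes, and no subgroup curves.
- *That the primary result is biased.* The test, the rate ratio and its interval do not use the height of the curve.

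**Conclusion.** The point holds as a minor improvement to a planned display. The direction is certain. The size, about 0.1-0.5 percentage points or roughly 1-4% relative for the composites, depends on the assumed N, event risk, share of competing deaths, follow-up time and constant hazards.

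The death count is itself uncertain. Footnote a to 4.2 excludes one centre from all analyses, and the SAP does not say whether the two participant counts treat that centre alike. If they do not, part of the gap is not deaths and the overstatement is smaller. It would also be smaller if the survivor count belonged to a date later than May 2016. No conclusion about efficacy changes.

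**What to change.** In section 5.1:

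1. Plot Aalen-Johansen cumulative incidence curves for the primary and secondary outcomes, with death outside the outcome as the competing event, instead of or beside the Kaplan-Meier curves. State for each outcome which deaths count as events and which compete; fatal presumed ischaemic stroke needs explicit mention.
2. Keep the log-rank tests and rate ratios unchanged, and caption each plot to say that the p-value compares cause-specific event rates.
3. Take any time-based absolute risk, absolute difference or number needed to treat from the cumulative incidence curves.

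The cost is a few sentences of text and standard software, with no new data. The plotted risks become slightly lower, and the caption is necessary because the log-rank test is not the test of those curves.

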5.2 Allowance for multiplicity of comparisons

The primary outcome will be assessed without adjustment for multiplicity. If a significant difference is demonstrated, then the key secondary outcome (i.e. major atherosclerotic events) and each of the components of the primary outcome (coronary death, myocardial infarction, and coronary revascularization) will be tested without adjustment. If a significant difference is demonstrated in the key secondary outcome, then presumed ischaemic stroke will be assessed. The remaining secondary outcome of major vascular events and the two additional composite outcomes requested by regulatory agencies (section 4.3) will be assessed without adjustment for multiplicity.

If there is directional consistency in the effect of the treatment on the primary outcome and on presumed ischaemic stroke, emphasis will be placed on the subgroup analyses for the secondary outcome of major vascular event (which incorporates both outcomes).

For tertiary, additional pre-specified and exploratory analyses (as noted in section 4.7), allowance in their interpretation will be made for multiple hypothesis testing,^{2,3} taking into account the nature of events (including timing, duration and severity) and evidence from other studies. In addition to the pre-specified comparisons, many other analyses will be performed with due allowance for their exploratory and, perhaps, data-dependent nature. Conventionally, two-sided P-values <0.05 are often described as “significant”. But, the larger the number of events on which a comparison is based and the more extreme the P-value after any allowance has been made for the nature of the particular comparison (i.e. primary, secondary or tertiary; pre-specified or exploratory), the more reliable the comparison and, hence, the more definite any finding will be considered. Analyses of fatal events will be interpreted in the light of the observed effects on relevant non-fatal events.³

5.3 Tests for heterogeneity of effects

Tests for heterogeneity of the proportional effect observed in subgroups will be used (whilst controlling the false discovery rate to allow for multiple comparisons) to determine whether the proportional effects in specific subcategories are clearly different from the overall effect.^{2,3} If, however, patient categories can be arranged in some meaningful order (e.g. age at randomization: <65; ≥65<70; ≥70) then assessment of any trend will be made. Unless otherwise stated, those with missing values of baseline values will be included in the subgroup that includes the median (for continuous variables) or the largest group (for categorical variables), and the number of missing values will be clearly indicated.

When a number of different subgroups are considered, chance alone may lead to there being no apparent effect in several subgroups in which the effect of treatment really is about the same as is observed overall. In such circumstances, “lack of direct evidence of benefit” is not good “evidence of lack of benefit”, and clearly significant overall results would provide strong indirect evidence of benefit in some small subgroups where the results, considered in isolation, are not conventionally significant (or, even, perhaps, slightly adverse).^{2,3,5} Hence, unless the proportional effect in some specific subcategory is clearly different from that observed overall, the effect in that subcategory is likely to be best estimated indirectly by applying the proportional effect observed among all patients in the trial to the absolute risk of the event observed among control patients in that category.⁵

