4.4 Tertiary assessments

Tertiary assessments will involve intention-to-treat analyses among all randomized participants of the effects of allocation to anacetrapib versus placebo during the scheduled treatment period on:

- (i) Coronary death or myocardial infarction, and, separately, myocardial infarction alone
- (ii) Mortality
 - from all causes combined; and, separately, within particular categories of causes, i.e.:
 - all cardiovascular causes combined; and, separately:
 - coronary (including sudden cardiac death)
 - other cardiac
 - stroke
 - other vascular
 - all non-cardiovascular causes combined; and, separately:
 - cancer
 - infection
 - respiratory
 - hepatic
 - other medical*
 - non-medical

* including undetermined cause

- (iii) Stroke
 - of any type combined; and, separately, of particular types, i.e.:
 - confirmed ischaemic stroke
 - confirmed haemorrhagic stroke
 - stroke of unknown/unconfirmed aetiology
- (iv) Major coronary events, major atherosclerotic events, and major vascular events, separately, in various subdivisions:
 - (a) occurring more than one year after randomization;
 - (b) disease type prior to randomization:
 - coronary heart disease
 - cerebrovascular disease

REVEAL Data Analysis Plan

- peripheral arterial disease
- diabetes*

and timing of most recent qualifying vascular event: <12; ≥12 months

* diabetes at randomization is defined as self-reported diabetes recorded on screening or randomization form; or diabetes-related adverse event recorded on or before date of randomization; or use of hypoglycaemic medication reported on randomization form

(c) three similar-sized groups based on lipid and lipoprotein measurements* from the Randomization visit:

- HDL cholesterol (mmol/L): <0.9; ≥0.9<1.1; ≥1.1
- LDL cholesterol (mmol/L): <1.4; ≥1.4<1.7; ≥1.7
- total cholesterol (mmol/L): <3.2; ≥3.2<3.7; ≥3.7
- non-HDL cholesterol (mmol/L): <2.2; ≥2.2<2.6; ≥2.6
- triglycerides (mmol/L): <1.2; ≥1.2<1.7; ≥1.7
- apolipoprotein B (mg/dL): <60; ≥60<70; ≥70
- apolipoprotein A1 (mg/dL) <110; ≥110<125; ≥125
- lipoprotein (a) (nmol/L): <15; ≥15<55; ≥55

* using results measured in the central laboratory

(d) various other categories of participant based on their Randomization visit values:

- age (years): <65; ≥65<70; ≥70
- sex: male; female
- region: North America; Europe; Asia
- blood pressure (mmHg):
 - systolic <125; ≥125<140; ≥140
 - diastolic <75; ≥75<85; ≥85
- kidney function

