 - estimated Glomerular Filtration Rate (ml/min/1.73m²) derived using the CKD-EPI equation⁴: <60; ≥60
 - urinary albumin:creatinine ratio (mg/mmol): normo-albuminuria (<3); micro-albuminuria (≥3 <30); macro-albuminuria (≥30)
- alcohol intake: current drinker; former/never drinker
- cigarette smoking: current; former; never
- body mass index (kg/m²): <25; ≥25<30; ≥30
- waist:hip ratio: low (<0.87 in women; <0.94 in men); medium (≥0.87<0.93 in women; ≥0.94<1.00 in men); high (≥0.93 in women; ≥1.00 in men)
- history of heart failure: yes; no
- atorvastatin dose (mg): low (10 in China; 20 in rest of the world); high (20 in China; 80 in rest of the world)

(e) presence and absence of other treatments used at the Randomization visit:

- angiotensin-converting-enzyme inhibitors or angiotensin-receptor blockers:
- aspirin or other antiplatelet drugs
- diuretics
- calcium-channel blockers
- beta-blockers

(v) Urgent and non-urgent coronary revascularization, considered separately and combined;

(vi) Non-coronary revascularizations, including percutaneous interventions (with or without stenting), surgical revascularization procedures (e.g. grafting, endarterectomy), and amputation for presumed vascular disease;

- (vii) Hospitalization for heart failure;
- (viii) Development of diabetes mellitus* among those not known to be diabetic at randomization (see section 4.4.iv.b);
 - * development of diabetes is defined as a post-randomization diabetes-related adverse event; or use of hypoglycaemic medication reported on at least one follow-up form
- (ix) Combination of first and subsequent occurrences of the primary outcome;
- (x) Cancer (fatal or non-fatal combined, and excluding any known to pre-date randomization and non-melanoma skin cancers)
 - at all sites combined; and, separately, at particular sites
 - gastrointestinal
 - respiratory
 - breast
 - melanoma
 - genitourinary
 - haematological
 - other or not specified
- (xi) Serious adverse events (overall and by subtype) due to:
 - Infection at all sites combined; and, separately, at particular sites:
 - Respiratory
 - Renal and urinary
 - Gastrointestinal
 - Skin
 - Systemic (including septicaemia)
 - Other or unspecified
 - Respiratory disease of all types combined; and, separately, of particular types:
 - Bronchial
 - Pulmonary vascular
 - Pleural
 - Other lower respiratory tract
 - Upper respiratory tract
 - Other respiratory

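### Does placing participants with a missing baseline value in the median or largest subgroup distort the subgroup results?

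*SAP*

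**What the plan says.** Section 5.3 of the SAP sets a default for every subgroup factor: "those with missing values of baseline values will be included in the subgroup that includes the median (for continuous variables) or the largest group" (the latter for categorical variables). It adds that "the number of missing values will be clearly indicated". Section 4.4(iv), which lists the factors, makes no exception.

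Two other parts of section 5.3 bear on the point. The first concerns testing: "Tests for heterogeneity of the proportional effect observed in subgroups will be used (whilst controlling the false discovery rate" to allow for multiple comparisons), with an assessment of trend where categories have a meaningful order. The second concerns estimation. Unless a category clearly differs from the whole, its effect is likely to be best estimated by "applying the proportional effect observed among all patients in the trial to the absolute risk of the event observed among control patients in that category".

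The factors include lipid variables cut into "three similar-sized groups based on lipid and lipoprotein measurements" (section 4.4(iv)(c)), and others with unequal or two-level splits (section 4.4(iv)(d) and (e)). Section 4.6 says the lipid assays use "non-fasting specimens taken from all participants at the randomization visit". The SAP gives no figure for missing baseline values.

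**The concern.** The rule puts people whose category is unknown into a named category and then treats them as members. Two consequences suggest themselves.

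- **Control risk.** Section 5.3 uses the "absolute risk of the event observed among control patients in that category" as an input to its preferred subgroup estimate. If people with missing values have a different risk, that input is shifted. Reporting the number missing shows how large the mixture is but does not remove it.
- **Heterogeneity tests.** Adding people from all categories to one of them pulls its rate ratio towards the average and so weakens the test.

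The SAP plans no analysis restricted to known values. Section 5.1 declines informative-missingness analyses because loss to follow-up is low, which concerns outcomes and not baseline values. At stake would be the rate and rate ratio shown for the receiving category of each factor.

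**Working it through.** The SAP states no figure on this point, so there is nothing to reproduce. Everything below rests on assumed inputs.

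**Inputs**
- m, share with a missing value: assumed 1%, 2%, 5%, 10%.
- c, share of known values in the receiving category: 1/3 for the lipid thirds (section 4.4(iv)(c)); 60% and 70% assumed for a majority group.
- RR, risk of those with missing values relative to known members: assumed 1.5 (1.25 gives about half the shifts).
- Missingness unrelated to the true category: assumed.

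**Step 1. Share of unknowns in the receiving category**

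s = m / (m + (1 − m)c)

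For a third with 5% missing, s = 0.05 / (0.05 + 0.95/3) = 0.136. At 1%, 2% and 10% missing, s is 0.029, 0.058 and 0.250.

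**Step 2. Shift measured against known members only**

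The shift is s(RR − 1), which at 5% missing is 0.136 × 0.5 = 6.8%. This is the figure that makes the rule look poor. It takes the known members as the truth, but the category's real population also includes the people with missing values who belong to it.

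**Step 3. Shift measured against the whole category**

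- True category risk, relative to known members: 1 + m(RR − 1).
- SAP rule: [1 + s(RR − 1)] / [1 + m(RR − 1)] − 1.
- Exclusion: 1 / [1 + m(RR − 1)] − 1.

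For a third with 5% missing, the SAP rule gives 1.068/1.025 − 1 = +4.2% and exclusion gives 1/1.025 − 1 = −2.4%.

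| Bias in control risk, RR 1.5 | 1% missing | 5% missing | 10% missing |
|---|---|---|---|
| SAP rule, middle third | +1.0% | +4.2% | +7.1% |
| SAP rule, 60% group | +0.3% | +1.5% | +2.7% |
| SAP rule, 70% group | +0.2% | +1.0% | +1.8% |
| Exclusion, any group | −0.5% | −2.4% | −4.8% |

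Exclusion does not remove the bias; it reverses the sign. The SAP rule has the smaller bias when s < 2m, that is, when c > (0.5 − m)/(1 − m). That threshold is 0.495 at 1% missing and 0.474 at 5%, so roughly whenever the receiving group holds half or more of participants. For a middle third, exclusion has the smaller bias.

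**Step 4. Comparison with sampling error**

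With an assumed 3,500 events in total, a control-arm third has about 3,500/6 = 583 events. The relative standard error is about 1/√583 = 4.1%. At 1–2% missing, the middle-third bias under the SAP rule is +1.0% to +1.9%, well inside that.

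**Step 5. Heterogeneity and trend tests**

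Assume hazard ratios running from 0.85 to 0.98, people with missing values having the overall mix and average risk, and variance proportional to 1/n. The table gives the z-statistic under the SAP rule divided by z under exclusion.

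| Factor | 1% | 2% | 5% | 10% |
|---|---|---|---|---|
| Two levels, 60:40 | 0.997 | 0.993 | 0.984 | 0.968 |
| Ordered 70:25:5, trend, missing placed in the first category | 0.998 | 0.996 | 0.991 | 0.982 |
| Equal thirds, trend, missing placed in the middle | 1.000 | 1.000 | 1.000 | 1.000 |

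As a check on the first row: at 10% missing the retained log hazard ratio difference is 1 − 0.04/0.64 = 0.9375. Part of that loss is recovered because the SAP rule keeps more participants, which gives 0.968.

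**Step 6. What cannot be affected**

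The value is fixed at or before randomization, and the rule makes no reference to treatment or outcome. Each category, mixture or not, is therefore still a randomized comparison. The overall primary and secondary analyses do not use these categories.

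**The case for a change.** The best case for the concern is that the description of the rule is accurate, the direction of both effects is right, and a separate row for missing values would cost little. The losses can also be larger than those in the last table. If only the receiving third differs (hazard ratios 0.97, 0.78, 0.97) and a general heterogeneity test is used with 3,500 assumed events, power at average risk is 76.9% under the rule against 77.8% on known values at 1% missing. At 5% it is 71.6% against 76.0%. With those missing at twice the risk, the gap reaches 8 points at 5% missing and 14 points at 10%. Section 5.2 also gives the subgroup analyses of major vascular events some prominence if the effects on the primary outcome and on presumed ischaemic stroke agree in direction.

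Part of this stands. An unordered factor with substantial missingness and an effect peculiar to the receiving category would lose some power, and for a middle third the control risk is better estimated from known members. But section 5.3 calls for trend assessment in ordered categories such as the lipid thirds, where a linear trend loses nothing. Nothing in the SAP supports 5–10% missing. Section 4.6 has specimens taken from every participant at randomization, which points to low missingness for lipids, and section 4.4(iv)(b) defines diabetes by the presence of a record, which leaves no obvious missing category. Exclusion has its own price: about 300 of 30,000 participants per factor at 1% missing and 1,500–3,000 at 5–10%, in analyses that section 4.4 specifies among all randomized participants.

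**Conclusion.** The concern does not hold. Section 5.3 fixes in advance a simple rule that is blind to treatment and outcome, and commits to showing how many participants it affects. It contradicts nothing else in the SAP and leaves the randomized comparisons valid.

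At 1–2% missing and 1.5 times the risk, the control-risk bias is at most about 2% in a middle third and 0.2–0.6% in a 60–70% group. The loss in the test statistic is 0.2–0.7% for the two-level and skewed ordered factors examined, and nil for a trend over equal thirds. Excluding those participants would give a larger bias wherever the receiving group holds about half or more of participants. A known-values analysis would be a harmless addition, but its absence is not a fault.

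This rests on baseline missingness being low, which the SAP suggests for lipids but does not quantify, and on missingness being unrelated to the true category. If 5% or more were missing for an unordered factor, the reported count would show it and that factor would deserve a second look.
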